To calculate the sample size, we estimated that only 10% of participants in the placebo group will have a parasitemia below the microscopic limit of detection on day 7 versus 50% in the intervention group. With a power of 80% and an alpha error of 5% and considering a ratio 1:1 (treatment versus placebo group), we need 20 subjects in the placebo group and 20 subjects in intervention group. Accounting for a possible dropout rate of 10% in each study arm the final sample size will require recruitment of a total of 44 subjects.

Endpoints and assessment methods

Primary endpoint:

Parasitemia undetectable by thick blood smear on D7 after the start of administration of study drugs

Assessment method: Light microscopy

All those needing rescue treatment according to the physicians' judgement before day 7 will be counted as treatment failures together with all positives at day 7.

Secondary endpoints:

1) Parasitemia reduction $\geq 90\%$ on D7 compared with baseline assessed by light microscopy of thick blood smears

Assessment method: Light microscopy

2a) Time to parasitemia level < 100 parasites/ μl in the PZQ 3-day treatment group versus placebo assessed by microscopy

Assessment method: Light microscopy

2b) Time to parasitemia level below microscopic limit of detection in the PZQ 3-day treatment group versus placebo assessed by microscopy

Assessment method: Light microscopy

3) Occurrence of adverse events (AEs) in the PZQ 3-day treatment group versus placebo

Assessment method: Clinical examination and laboratory analysis

4) Time to parasite clearance assessed by qPCR in the PZQ 3-day treatment group versus placebo

Assessment method: Quantitative PCR

5) Parasitological cure rate assessed by qPCR on D7 after administration of study drugs

Assessment method: Quantitative PCR

6) Area under the curve (AUC) of microscopically-determined parasite mass between D0 and D7 in the PZQ 3-day treatment group versus placebo

Assessment method: Light microscopy

Exploratory endpoints

Proportion of participants with detectable gametocytes during D3-D7 in the treatment group versus placebo

Assessment method: Light microscopy

Duration of the study

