Participants fulfilling all inclusion/exclusion criteria will be randomly allocated to receive either placebo once-daily dosing for 3 days, or PZQ 40mg/kg once-daily dosing for 3 days. The allocation ratio is 1:1. Randomization lists will be created using permuted blocks. Treatment allocation codes will be stored in opaque-sealed envelopes on whose surface is a pre-defined allocation sequence number. Each time a participant fulfils the inclusion criteria the opaque-sealed envelope with the next allocation sequence number is opened by the pharmacist or his delegate. During the treatment period all participants will be hospitalized for three days. Study procedures during the treatment period and follow-up visit will be the same in the two study arms.

Study procedures

Blinding

Laboratory investigators processing and analysing biological samples will be blinded to group allocation. The unblinded pharmacist or designate will prepare the treatment assigned by the randomization system and complete the corresponding treatment record form. Subsequently, verum and placebo will be administered by a physician who is not involved in diagnostic and analytic processes of the study. Other study physicians and study participants will be unaware of group allocation. Only the pharmacists and the physician administering verum and placebo know the group allocation. Verum and placebo are similar but not identical and will be administered to each participant separately out of the original packaging without changing labels.

Procedures will be performed at the time points indicated in the schedule of procedures (Table 2). Additional procedures or laboratory tests may be performed at any time, at the discretion of the investigators if clinically necessary.

Ascertainment of basic demographic information, clinical and past medical history

- Full medical history
- Prior concomitant medication
- Demographic data (gender, age)
- Clinical examination (including measurement of height and weight)
- Vital signs (including pulse, blood pressure and body temperature)

Blood sampling and laboratory tests

A series of blood samples will be drawn to perform different tests. Types of tests to be performed include molecular biology, biochemistry, haematology and parasitology.

Details of these tests are as follows:

Parasitology:

These tests include thick and thin blood smears and qPCR to detect the malaria parasite.

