Generally, 'ULN = Upper Limit of Normal' and 'LLN = Lower Limit of Normal' are given to grade adverse events. Thereby usage of different blood value units in different laboratories can be largely respected. In the rare case that international grading classification systems used only one specific blood value unit (which might not be used in a given laboratory) investigators are asked to do the following: convert the result as given by your local laboratory to a result (and unit) which is required to adequately grade the abnormal laboratory value. Afterwards grade the adverse event based on the converted result by using adequate tables below. This approach will ensure timely grading of adverse events. Any method/source deemed appropriate by expert study staff can be used for conversion.

Statistics

Data analysis will consist of descriptive summaries for treatment groups. The primary endpoint of successful clearance of *Plasmodium falciparum* infection on Day 7 will be assessed for each patient and the number and percent of participants achieving this endpoint summarised for each group. Chi-square tests will be used for hypothesis testing between study groups.

For secondary endpoints descriptive summaries and plots over the time course for both individual patient results and groups will be presented. Where appropriate numbers and percent of participants achieving the given endpoint will be presented per group. Where appropriate highly skewed data will be log-transformed and presented as geometric means with 95% confidence intervals. Time to event data will be described using the Kaplan-Meier method and if appropriate by Cox proportional hazards models. Area under the curve (AUC) will be computed using the trapezoidal rule.

Quality control and quality assurance procedures

Monitoring

Monitoring will be performed according to ICH Good Clinical Practice (GCP) by a monitor who is independent from the study. The monitor will verify that the clinical trial is conducted and data are generated, documented and reported in compliance with the protocol, GCP and the applicable regulatory requirements. The investigators will provide direct access to all trial related source data/documents and reports for the purpose of monitoring and auditing by the sponsor and inspection by local and regulatory authorities.

Medical monitor

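### The primary day 7 clearance test is valid and adequately powered, but it makes no use of baseline parasite density, a plausibly prognostic covariate already measured at H0

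*Protocol*

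**What the plan says.** The primary endpoint (Protocol, Endpoints and assessment methods) is "Parasitemia undetectable by thick blood smear on D7 after the start of administration of study drugs". Participants given rescue treatment before day 7 count as failures, so the outcome is binary.

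The Statistics section summarises this endpoint by number and percentage in each group and adds "Chi-square tests will be used for hypothesis testing between study groups". It names no covariate for this comparison.

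Under Allocation of the groups, the protocol says "Randomization lists will be created using permuted blocks". It mentions no stratification factor.

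Eligibility admits densities from 200 to 5000 parasites/µL. Thick smears quantify density at screening and again at H0 before the first dose (Blood sampling and laboratory tests; Study drug administration). Baseline density does enter the plan elsewhere: secondary endpoint 1 is a reduction of at least 90% from baseline, and secondary objective 6 concerns parasite mass adjusted for baseline.

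**The concern.** Success is defined by a fixed limit of detection. For any limit L, a participant entering at 5000/µL needs a fold reduction of 5000/L and one entering at 200/µL needs 200/L. The ratio is 25 whatever L is. It is therefore reasonable to expect entry density to carry some information about day 7 status. Neither the allocation nor the primary test uses it.

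Two things are at stake in a trial of 22 per arm. If density is prognostic, the unadjusted comparison gives up precision that the collected data could supply. And if the arms happen to differ in density, the unadjusted result of this one trial cannot be corrected for that, while an adjusted analysis chosen after seeing the imbalance would be open to challenge.

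**Working it through.** **Reproducing the plan's own figure.** The inputs, from Sample size, are success rates of 0.10 on placebo and 0.50 on praziquantel, 80% power, alpha 5% and equal arms. The protocol does not say whether alpha is two-sided; two-sided reproduces its number. With the pooled rate (0.10 + 0.50)/2 = 0.30 and no continuity correction:

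n = [1.960·√(2·0.3·0.7) + 0.842·√(0.1·0.9 + 0.5·0.5)]² / 0.4² = (1.270 + 0.491)² / 0.16 = 19.4, rounded up to 20 per arm.

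This agrees with "we need 20 subjects in the placebo group and 20 subjects in intervention group". The 10% dropout allowance gives 40 × 1.1 = 44.

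**The named test as it stands.** Exact binomial enumeration for the uncorrected chi-square gives power of 0.838 at 20 per arm and 0.864 at 22. At 20 per arm its type I error is 0.039 (10% in both arms), 0.053 (30%) and 0.043 (50%). So it is valid and above target. With a continuity correction, power at 20 per arm would be 0.726; the sample size fits the uncorrected form.

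**Likely size of a chance imbalance.** The documents give no density distribution, so log-uniform on 200-5000 is assumed.
- SD of log10 density = log10(25)/√12 = 1.398/3.464 = 0.404.
- SE of the difference between arms at 20 per arm = 0.404·√(2/20) = 0.128.
- One SE is a ratio of geometric means of 10^0.128 = 1.34. The 95% range reaches 10^(1.96·0.128) = 1.78-fold.

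**Adjusted against unadjusted.** Trials were simulated at 20 per arm (20,000 or more per row). The outcome was logistic in log10 density, with overall rates held at 10% and 50%. The comparison is Pearson chi-square against an ordinary linear model with arm and log10 density, using the t test for the arm coefficient. The slope is not in the documents, so a range is shown. The second column translates each slope into clearance in the praziquantel arm at the two ends of the entry range.

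| Log-odds slope per log10 density | Praziquantel clearance at 200 v 5000/µL | Power, chi-square | Power, adjusted | Change |
|---|---|---|---|---|
| 0 | 50% v 50% | 0.84 | 0.82 | about -2 points |
| -1.5 | 74% v 26% | 0.84 | 0.84-0.85 | about 0 to +1 |
| -3 | 89% v 11% | 0.84 | 0.89 | about +5 |
| -4.5 | 96% v 4% | 0.84 | 0.93 | about +9 |

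Type I error of the linear model was about 0.04 at 10% in both arms and 0.05 at 30% in both arms, at every slope.

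**When imbalance occurs.** In about 16% of trials, mean log10 density in the praziquantel arm exceeds that in the placebo arm by more than one SE. In those trials (figures good to about 0.02):

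| Slope | Chi-square power | Adjusted power |
|---|---|---|
| -1.5 | 0.74 | 0.82 |
| -3 | 0.65 | 0.87 |
| -4.5 | 0.58 | 0.91-0.92 |

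With 30% in both arms and an imbalance above one SE in either direction, the chi-square's conditional type I error is about 0.06, 0.09 and 0.11 at these slopes. The adjusted test stays at about 0.05.

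**The case against.** The strongest reply is that nothing here is wrong. The chi-square is valid under randomisation, agrees with the sample-size calculation and exceeds its target power. Chance imbalance is already part of its overall error rate: across all simulated trials its type I error does not rise with the slope. A statistical analysis plan, not shown, may add an adjusted analysis. All of this stands, and it limits the point to a missed gain in precision.

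A reader might infer that density is the main determinant of day 7 status. The documents do not say so. In the only data they give on density after praziquantel alone (the school-children trial in the background section), mean density fell from 3249 to 711/µL while prevalence went from 81% to 86%, which shows no relation between entry density and clearance. With a parent half-life of 0.8 to 1.5 hours, a last dose at H48, and mouse parasitaemia that rose again after treatment stopped, day 7 status may also reflect regrowth. The relation is plausible and no more.

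A reader might also infer that the plan yields a p-value with no effect estimate. It does not: the percentages per arm give the risk difference directly.

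Finally, adjustment can be done badly with about 2 + 10 = 12 expected successes. An ordinary logistic likelihood-ratio test adjusted for density had type I error of about 8-9% at 10% in both arms. That argues for naming the model in advance; it does not apply to the linear model checked above.

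**Conclusion.** The point holds as an inexpensive improvement to a valid primary analysis. It is neither an error nor a contradiction. The use of baseline in secondary endpoint 1 and secondary objective 6 does not conflict with an unadjusted primary test.

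Averaged over all trials, the effect on power is small to moderate: a loss of about 2 points if density is unrelated to clearance, almost nothing at a slope that already implies 74% v 26% clearance across the entry range, and 5 to 9 points only at steeper slopes. The better argument is protection when the arms differ in density by chance, where the unadjusted test loses 8 points or more of power at slopes of -1.5 and beyond (0.82 - 0.74 = 0.08 at -1.5).

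These figures rest on log-uniform density, a logistic relation of assumed slope, and the protocol's 10% and 50%. Power and type I error were checked for the linear model; coverage of its confidence interval was not.

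**What to change.** Before unblinding, fix one primary model: day 7 clearance (0/1, rescue before day 7 counted as failure) regressed linearly on arm and log10 H0 density, with no other covariate. The arm coefficient is the adjusted risk difference, to be reported with its 95% CI and the t test. State that the supporting unadjusted test is the chi-square without continuity correction. Name this single model and do not leave a choice of methods open.

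No new data are needed, since H0 density is already collected. The work is a short addition to the Statistics section, or to the analysis plan with a note that it supersedes the test named in the protocol. The price is about 2 points of power if density proves unrelated to clearance. If the sponsor prefers to keep the chi-square as primary, the same model should at least be pre-specified as supportive, so that adjustment is not decided after an imbalance has been seen.

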Annex 1: Grading of abnormal lab values which are ‘not clinically significant’

Laboratory values and grading:

Table 5 Biochemistry Values and Grading

	Biochemistry (modified CTCAE v5)			
Variable	Grade 1	Moderate Grade 2	Severe Grade 3	Potentially Life Threatening Grade 4
ALT (GPT)	None	>3.0 – 5.0 ULN if baseline was normal; baseline was normal; >3.0 – 5.0 x baseline if baseline was abnormal	>5.0 – 20.0 x ULN if baseline was normal; baseline was normal; >5.0 – 20.0 x baseline if baseline was abnormal	> 20.0 x ULN if baseline was normal; baseline was normal; > 20.0 x baseline if baseline was abnormal
AST (GOT)	None	>3.0 – 5.0 ULN if baseline was normal; >3.0 – 5.0 x baseline if baseline was abnormal	>5.0 – 20.0 x ULN if baseline was normal; baseline was normal; >5.0 – 20.0 x baseline if baseline was abnormal	> 20.0 x ULN if baseline was normal; baseline was normal; > 20.0 x baseline if baseline was abnormal
Alkaline Phosphatase	None	>2.5 – 5.0 ULN if baseline was normal; >2.5 – 5.0 x baseline if baseline was abnormal	>5.0 – 20.0 x ULN if baseline was normal; baseline was normal; >5.0 – 20.0 x baseline if baseline was abnormal	> 20.0 x ULN if baseline was normal; baseline was normal; > 20.0 x baseline if baseline was abnormal
Total Bilirubin	None	>1.5 – 3.0 ULN if baseline was normal; >1.5 – 3.0 x baseline if baseline was abnormal	>3.0 – 10.0 x ULN if baseline was normal; baseline was normal; >3.0 – 10.0 x baseline if baseline was abnormal	> 10.0 x ULN if baseline was normal; baseline was normal; > 10.0 x baseline if baseline was abnormal

Albumin	None	<3 - 2 g/dL; <30 - 20 g/L	<2 g/dL; <20 g/L	Life-threatening Death consequences; urgent intervention indicated
Creatine Kinase	None	>2.5 x ULN - 5 x ULN	>5 x ULN - 10 x ULN	>10 x ULN
Sodium (Hypernatremia)	None	>150 - 155 mmol/L; intervention initiated	>155 - 160 mmol/L; hospitalization indicated	>160 mmol/L; life-threatening consequences
Sodium (Hyponatremia)	None	125-129 mmol/L and asymptomatic	125-129 mmol/L symptomatic; 120-124 mmol/L regardless of symptoms	<120 mmol/L; life-threatening consequences
Glucose (Hyperglycemia)	None	Change in daily management from baseline for a diabetic; oral antiglycemic agent initiated; workup for diabetes	Insulin therapy initiated; hospitalization indicated	life-threatening consequences; urgent intervention indicated
Glucose (Hypoglycemia)	None	<55 - 40 mg/dL; <3.0 - 2.2 mmol/L	<40 - 30 mg/dL; <2.2 - 1.7 mmol/L	<30 mg/dL; <1.7 mmol/L; life-threatening consequences; seizures
LDH	None	>3 x ULN	-	-
Potassium (Hyperkalemia)	None	>5.5 - 6.0 mmol/L; intervention initiated	>6.0 - 7.0 mmol/L; hospitalization indicated	>7.0 mmol/L; life-threatening consequences
Potassium (Hypokalemia)	None	Symptomatic with <LLN - 3.0 mmol/L; intervention indicated	<3.0 - 2.5 mmol/L; hospitalization indicated	<2.5 mmol/L; life-threatening consequences

Creatinine	None	>1.5 - 3.0 x baseline; >1.5 - 3.0 x ULN	>3.0 x baseline; >3.0 - 6.0 x ULN	>6.0 x ULN
Urea* (Blood Nitrogen Urea [BUN])	None	2.6 - 5 x ULN	5.1 - 10 x ULN	> 10 x ULN

* Ranges for BUN taken from Division Of Microbiology And Infectious Diseases (DMID) as not available in CTCAE

v5

Laboratory values and grading:

Table 6 Hematology Values and Grading

	Haematology (modified CTCAE v5)			
Variable	Grade 1	Moderate Grade 2	Severe Grade 3	Potentially Life Threatening Grade 4
Haemoglobin	None		< 8.0 g/dL; < 4.9 mmol/L; < 80 g/L; transfusion indicated	Life-threatening consequences; urgent intervention indicated
Leukocytes (WBC) [decreased]	None	<3000 - 2000/mm ³ ; <3.0 - 2.0 x 10 ⁹ /L	<2000 - 1000/mm ³ ; <2.0 - 1.0 x 10 ⁹ /L	<1000/mm ³ ; <1.0 x 10 ⁹ /L
Leukocytes (WBC) [increased]	None	-	>100,000/mm ³	Clinical manifestations of leucostasis; urgent intervention indicated
Lymphocytes [decreased]	None	<800 - 500/mm ³ ; <0.8 - 0.5 x 10 ⁹ /L	<500 - 200/mm ³ ; <0.5 - 0.2 x 10 ⁹ /L	<200/mm ³ ; <0.2 x 10 ⁹ /L
Lymphocytes [increased]	None	>4000/mm ³ - 20,000/mm ³	>20,000/mm ³	-

Neutrophils [decreased]	None	<1500 - 1000/mm ³ ; <1.5 - 1.0 x 10 ⁹ /L	<1000 - 500/mm ³ ; <1.0 - 0.5 x 10 ⁹ /L	<500/mm ³ ; <0.5 x 10 ⁹ /L
Platelet count [decreased]	None		<50,000 - 25,000/mm ³ ; <50.0 - 25.0 x 10 ⁹ /L	<25,000/mm ³ ; <25.0 x 10 ⁹ /L
